Appendix C: Definition of Region Variable

The list of country, country code, and region variable are provided in [Table 11](#).

Table 11: Definition of Region Variable

COUNTRY	COUNTRY CODE	REGION VARIABLE
Australia	AUS	RoW
Belgium	BEL	EU
Canada	CAN	RoW
France	FRA	EU
Germany	DEU	EU
Israel	ISR	RoW
Italy	ITA	EU
Netherlands	NLD	EU
Poland	POL	EU
Saudi Arabia	SAU	RoW
Spain	ESP	EU
Sweden	SWE	EU
Turkey	TUR	RoW
United Kingdom	GBR	EU
United States	USA	US

EU: European Union; RoW: rest of world; US: United States

Appendix D: Handling of Missing or Incomplete Dates

Global Statement:

If the imputed date is prior to the date of birth, then impute the missing date as date of birth.

Imputation rules for missing or partial AE start date are defined below:

If only Day of AE start date is missing:

If the AE start year and month are the same as that for the first dose date, then:

- If the full (or partial) AE end date is NOT before the first dose date or AE end date is missing, then impute the AE start day as the day of first dose date

- If AE end date is prior to first dose date, then impute the AE start day as 1

If Day and Month of AE start date are missing:

If AE start year = first dose year, then:

- If the full (or partial) AE end date is NOT before the first dose date or AE end date is missing, then impute the AE start month and day as the month and day of first dose date
- If AE end date is prior to first dose date, then impute the AE start month as January and the day as 1

If Year of AE start date is missing:

If the year of AE start is missing or AE start date is completely missing, then query the site with no imputation. Also compare the full (or partial) AE end date to the first dose date. If the AE end date is before the first dose date, then the AE should be considered as a pre-treatment AE. Otherwise, the AE will be considered as TEAE.

Imputation rules for missing or partial non-study medication start/stop dates are defined below:

Missing or partial non-study medication start date:

- If only day is missing, use the first day of the month
- If day and month are both missing, use the first day of the year
- If day, month, and year are all missing, use the date of the day before the first dose date

Missing or partial non-study medication stop date:

- If only day is missing, use the last day of the month
- If day and month are both missing, use the last day of the year
- If day, month, and year are all missing, assign “continuing” status to stop date

Appendix E: Normal Reference Ranges of Vital Signs¹⁰
Table 12: Heart Rate by Age (Beats/Minute) Reference

AGE	AWAKE RATE
Infant (<1 year)	100-190
Toddler (1-2 years)	98-140
Preschool (3-5 years)	80-120
School-age (6-11 years)	75-118
Adolescent (12-15 years)	60-100
> 15 years	60-100

Table 13: Normal Respiratory Rate by Age (Breaths/Minute) Reference

AGE	RESPIRATORY RATE
Infants (<1 year)	30-53
Toddler (1-2 years)	22-37
Preschool (3-5 years)	20-28
School-age (6-11 years)	18-25
Adolescent (12-15 years)	12-20
>15 years	12-20

Table 14: Normal Blood Pressure by Age (mm Hg) Reference

AGE	SYSTOLIC PRESSURE	DIASTOLIC PRESSURE
Infant (<1 year)	72-104	37-56
Toddler (1-2 years)	86-106	42-63
Preschooler (3-5 years)	89-112	46-72
School-age (6-9 years)	97-115	57-76
Preadolescent (10-11 years)	102-120	61-80
Adolescent (12-15 years)	110-131	64-83
>15 years	90-120	50-80

¹⁰ Pediatric Vital Signs Reference Chart. Peds cases - Pediatrics for Medical Students - Developed by Chris Novak and Peter Gill for PedsCases.com April 21, 2016 (<http://www.pedscases.com/pediatric-vital-signsreference-Chart>).

Table 15: Normal Temperature Range by Method

METHOD	TEMPERATURE (°C)
Rectal	36.6-38
Ear	35.8-38
Oral	35.5-37.5
Axillary	36.5-37.5
Temporal/core ^a	35.8-38

^a In the eCRF core and temporal temperature measurements can be ticked as methods. Rectal and Tympanic (ear) fall in this group. Additionally, temporal temperature measurements (using a temperature scanner on the forehead)—approximate closely to core temperature measurements and therefore can be classified in this category. For that reason, the normal temperature range for core and temporal temperature measurements will be defined as described.

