9.7.3 Vital Sign Measurements

Descriptive statistics for vital signs (temperature, systolic blood pressure, diastolic blood pressure, heart rate, respiratory rate, weight, height/length, mid-arm circumference, and BMI) and changes from baseline in vital signs at each post-baseline visit will be presented in a summary table. The change to the last visit will also be summarised. A shift table for the number of patients with changes from baseline to the highest or lowest value ([Appendix E](#)) will be provided by cohort/treatment subgroup during the treatment period.

Vital signs data will be listed.

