Appendix A: Derived Variables

A list of derived variables for demographic and baseline characteristics, various duration derivations, drug compliance, baseline derivations, and other important derivations applicable for this study is presented in Table 3.

Table 3: Derived Variables for Demographic and Baseline Characteristics, Various Duration Derivations, Drug Compliance, Baseline Derivations, and Other Important Derivations

VARIABLES	FORMULA
Demographic and Baseline Characteristics	
Age at informed consent (in years)	Cohort 1: For patients not from France and Germany, age will be calculated based on date of birth. For patients from France and Germany, only birth year was collected, and July 1 was imputed in the eDC system. The CRF collected age months and age years are based on the imputed date of birth. For analysis purpose, age will be calculated based on collected age months and age years on the Study A4250-005 CRF or the external file (primary source). Cohort 2: For patients not from France and Germany, age will be calculated based on date of birth. For patients from France and Germany, only birth year was collected, and July 1 was imputed in the eDC system. The CRF collected age months and age years are based on the imputed date of birth. For analysis purpose, age will be calculated based on collected age months and age years on the Study A4250-008 CRF or the external file (primary source).
BMI (kg/m ²)	Weight (kg)/[height (m) ²]
PFIC diagnosis (in years)	Will be derived by SAS YRDIF function YRDIF (date of diagnosis of PFIC, date of informed consent, 'ACT/ACT')
Derivation of Duration	
Study day at any visit	Date of interest–date of first dose of study drug. One day is added if this difference is ≥ 0
Extent of exposure (days)	Date of last study drug intake–date of first study drug intake + 1
Drug Compliance	
Compliance based on CRF data	$100 \times [(\text{total number of capsules dispensed} - \text{total number of capsules returned}) / (\text{total number of capsules planned to be taken})]$. This will be considered as the primary compliance rate.
Compliance based on eDiary data up to week 24	$100 \times (\text{total number of capsules taken up to week 24}) / (\text{total number of capsules planned to be taken up to week 24})$.

VARIABLES	FORMULA

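### The vital-sign shift table takes the highest or lowest value while its normal limits change with age and method, so an abnormal value can be hidden by a more extreme normal one

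*SAP*

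**What the plan says.** SAP Section 9.7.3 covers "temperature, systolic blood pressure, diastolic blood pressure, heart rate, respiratory rate, weight, height/length, mid-arm circumference, and BMI". These are summarised by visit with descriptive statistics and changes from baseline, and they are listed. It then plans "A shift table for the number of patients with changes from baseline to the highest or lowest value", with a pointer to Appendix E, which "will be provided by cohort/treatment subgroup during the treatment period".

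Appendix E gives limits for five of these measures:

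- Table 12, "Heart Rate by Age (Beats/Minute) Reference": six age rows, the last two with identical limits.
- Table 13, "Normal Respiratory Rate by Age (Breaths/Minute) Reference": the same six age rows, the last two again identical.
- Table 14, "Normal Blood Pressure by Age (mm Hg) Reference": seven age rows, all different.
- Table 15, "Normal Temperature Range by Method": five methods, with upper limits of 37.5 or 38 °C and lower limits from 35.5 to 36.6 °C.

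Neither place says whether values are classified before or after the extreme is picked, which age chooses the row, or what happens when a patient's temperature is taken by more than one method. The only age derived in Appendix A is age at informed consent.

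**The concern.** With one fixed pair of limits, the highest value is also the value most likely to be high, so classifying only the extreme loses nothing. With moving limits that link breaks. The largest number can be normal for the age at which it was taken while a smaller, later number is high.

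Band changes are to be expected here. The planned age categories start below 6 months, treatment lasts 72 weeks, and an optional extension follows. This shift table is also the only planned vital-sign display that counts patients outside the normal range; the other summaries are of continuous values. A patient misplaced here is not counted as abnormal anywhere else in the vital-sign tables.

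**Working it through.** The SAP states no figure on this point, so there is none to reproduce. The inputs are Tables 12 to 15 and the rule in Section 9.7.3.

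**Step 1. Apply the literal rule with the row for age (or method) at measurement.**

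| Measure | First value | Second value | Extreme taken | Shown as | Classified first |
|---|---|---|---|---|---|
| Heart rate | 135 at 2 y 11 m, normal (98–140) | 128 at 3 y 1 m, high (>120) | highest 135 | normal | high |
| Respiratory rate | 35 at 2 y 11 m, normal (22–37) | 31 at 3 y 1 m, high (>28) | highest 35 | normal | high |
| Systolic pressure | 80 at 11 m, normal (72–104) | 84 at 14 m, low (<86) | lowest 80 | normal | low |
| Temperature, °C | ear 37.9, normal (35.8–38) | oral 37.7, high (>37.5) | highest 37.9 | normal | high |

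**Step 2. Where masking can occur.** Comparing neighbouring rows, it is possible at every age boundary for systolic and diastolic pressure. For heart and respiratory rate it is possible at every boundary except 12–15 to >15 years, where the limits are equal. Maskable high heart rates lie between 140 and 190 at 1–2 years, 120 and 140 at 3–5, 118 and 120 at 6–11, and 100 and 118 at 12–15. Oral or axillary temperatures between 37.5 and 38 °C can be masked by a rectal, ear or temporal/core reading.

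**Step 3. The other reading: age at consent fixes the row.** A child enrolled under 1 year with heart rate 150 at 14 months is judged against 190 and called normal; the row for that age has an upper limit of 140. A respiratory rate of 25 at 14 months, normal against 22–37, is called low against 30–53. Errors now go both ways. The temperature example is unchanged, because it does not involve age.

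**Step 4. How many patients change band.** 72 weeks = 72 × 7 / 365.25 = 1.38 years. With entry age uniform within a band, the share crossing is min(1, 1.38 / band width). For the heart-rate bands:

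- <1 year: 100%
- 1–2 years: 1.38/2 = 69%
- 3–5 years: 1.38/3 = 46%
- 6–11 years: 1.38/6 = 23%

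With entry age uniform from 0.5 to 6 years, the share is (0.5 + 1.38 + 1.38)/5.5 = 59%. From 0.5 to 18 years it is (0.5 + 3 × 1.38)/17.5, about 27%. The extension raises these.

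**Step 5. How often the extreme misses an abnormal value.** The SAP gives no vital-sign or age distribution, so this rests on simulation. Assumptions: 10 post-baseline visits to Week 72, within-patient correlation 0.4, SD 0.7 to 1.0 times a quarter of the band width, and the row set by age at measurement. The figures are shares of patients with at least one value abnormal for age whom the raw extreme shows as not abnormal.

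| Entry age and mean trajectory | Heart rate, high | Respiratory rate, high | Systolic, low |
|---|---|---|---|
| 0.5–6 y, mean smooth between band mid-points | 20–31% | 32–47% | 15–24% |
| 0.5–6 y, mean stepping at each band | 14–16% | 22–27% | 13–17% |
| 0.5–18 y, mean stepping at each band | 7–10% | 10–13% | 11–14% |

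As a share of all patients in the second scenario, the misses are about 0.3–2% for heart rate and systolic pressure, and 0.5–3.4% for respiratory rate.

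**The case against.** The strongest reply is that the SAP never says the raw extreme is classified after it is chosen. A programmer could classify each value first and tabulate the worst category, and the table would then be right. Section 1 puts table templates in a separate document, which may settle this. That stands as far as it goes: the order of steps is inferred. But the sentence in Section 9.7.3 names the highest or lowest value, not the worst category, so its plain reading is the one that can go wrong, and the row-selecting age is open in any case.

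Second, nothing is lost from the record, since by-visit summaries and listings remain. Section 4.4 makes treatment-emergent adverse events the primary safety analysis. This stands and limits the weight of the point.

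Third, the miss rates depend on chosen inputs. This also stands. The highest come from young entry ages and a smooth mean, where many simulated abnormal values arise just after the limit steps down. The temperature example needs the method to vary within a patient, and the SAP does not say how often it does.

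A reader might infer two stronger things:

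- **That the table will understate harm.** The documents do not support this. Masking needs a patient who changes band or method and has values in the ranges above, and with a consent-age row some normal values would be called low.
- **That the laboratory shift tables share the defect.** Section 9.7.2 also uses the highest and lowest values, but with ranges supplied by the laboratories, and the SAP does not say that these vary with age.

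**Conclusion.** The point holds as a possibility created by the wording: abnormal values can be hidden, not that they will be. With the row set by age at measurement and the extreme classified afterwards, masking only removes abnormal findings, because any extreme that is itself out of range would also be flagged by classifying first. With the row fixed by age at consent, children who change band are misclassified in either direction. Masking between temperature methods is possible under both.

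The size is uncertain. Across the scenarios tried, about 7% to 31% of patients with a high heart rate for age would be missed, 10% to 47% for respiratory rate and 11% to 24% for low systolic pressure. These figures depend on the assumed entry ages, mean trajectory, variability and correlation, none of which the SAP supplies. No efficacy result is touched. The change is worth making because it is nearly free and corrects the one display that counts out-of-range vital signs.

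**What to change.** In Section 9.7.3 and Appendix E, state that every vital-sign value is first classified as low, normal or high against the row for the patient's age on the day of measurement and, for temperature, the method used that day. Then cross-tabulate baseline category by worst post-baseline category, separately for any high and any low, in place of classifying the single highest and lowest values. Add age at measurement to Appendix A.

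The cost is a sentence or two, one derived variable and a change in the order of two programming steps. No new data are needed, and a few more patients may be flagged. For patients in France and Germany, where only birth year is collected and Appendix A takes age from recorded months and years, age at measurement can be that recorded age plus elapsed time; band changes there will be dated only as precisely as the recorded age allows.

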Appendix F: SI and US Conventional Units of Clinical Laboratory Values

SERUM CHEMISTRY	SI UNIT	CONVENTIONAL UNIT
Analyte		
Alpha Fetoprotein	IU/mL	ng/mL
Direct bilirubin	µmol/L	mg/dL
Calcium	mmol/L	mg/dL
Chloride	mmol/L	mEq/L
Creatinine	µmol/L	mg/dL
Potassium	mmol/L	mEq/L
Sodium	mmol/L	mEq/L
Serum bile acid	µmol/L	µg/mL
Total bilirubin	µmol/L	mg/dL
Haematology		
	SI Unit	Conventional Unit
Analyte		
Haematocrit	ratio (L/L)	%
Haemoglobin	g/L	g/dL
Red blood count (RBC)	$\times 10^{12}/L$	$\times 10^6/\mu L$
Platelet count	$\times 10^9/L$	$\times 10^3/\mu L$
White blood cell count	$\times 10^9/L$	$\times 10^3/\mu L$
Fat Soluble Vitamins		
Vitamin A	µmol/L	ug/dL
Vitamin E	µmol/L	mg/L
Vitamin D (25-dihydroxy)	nmol/L	ng/mL
Vitamin K	nmol/L	ng/mL
Urinalysis		
	SI Unit	Conventional Unit
Analyte		
Glucose	mmol/L	mg/dL
Ketones	mmol/L	mg/dL
Protein	mmol/L	mg/dL

Appendix G: PT Term of Possible Sequelae of FSV Deficiency

PT Term	Code
Acetabulum fracture	10000397
Activated partial thromboplastin time abnormal	10000631
Activated partial thromboplastin time prolonged	10000636
Adrenal haemorrhage	10001361
Alopecia	10001760
Anastomotic ulcer haemorrhage	10002244
Ankle fracture	10002544
Aortic aneurysm rupture	10002886
Areflexia	10003084
Arrhythmia	10003119
Arterial rupture	10003173
Auricular haematoma	10003797
Bleeding varicose vein	10005144
Blindness	10005169
Blindness transient	10005184
Blood blister	10005372
Blood calcium decreased	10005395
Blood urine	10005863
Bone pain	10006002
Brain stem haemorrhage	10006145
Breast haemorrhage	10006254
Broad ligament haematoma	10006375
Calcium deficiency	10006956
Cephalhaematoma	10008014
Cerebellar haemorrhage	10008030
Cerebral aneurysm ruptured syphilitic	10008076
Cerebral arteriovenous malformation haemorrhagic	10008086
Cerebral haemorrhage	10008111
Cerebral haemorrhage neonatal	10008112
Choroidal haemorrhage	10008786
Clavicle fracture	10009245
Closed fracture manipulation	10009506
Coagulation factor IX level decreased	10009746
Coagulation factor VII level decreased	10009761
Coagulation factor X level decreased	10009775
Coagulation time prolonged	10009799

PT Term	Code
Coagulopathy	10009802
Colonic haematoma	10009996
Complicated fracture	10010149
Compression fracture	10010214
Congenital anomaly	10010356
Conjunctival haemorrhage	10010719
Corneal scar	10011044
Cystitis haemorrhagic	10011793
Decreased immune responsiveness	10011968
Dementia	10012267
Dental caries	10012318
Diarrhoea haemorrhagic	10012741
Disseminated intravascular coagulation	10013442
Diverticulitis intestinal haemorrhagic	10013541
Diverticulum intestinal haemorrhagic	10013560
Dry eye	10013774
Duodenal ulcer haemorrhage	10013839
Duodenitis haemorrhagic	10013865
Dwarfism	10013883
Dysarthria	10013887
Dysphagia	10013950
Ear haemorrhage	10014009
Eccymosis	10014080
Encephalitis haemorrhagic	10014589
Enterocolitis haemorrhagic	10014896
Epistaxis	10015090
Exsanguination	10015719
External fixation of fracture	10015741
Extradural haematoma	10015769
Extravasation blood	10015867
Eye haemorrhage	10015926
Factor IX deficiency	10016077
Femoral neck fracture	10016450
Femur fracture	10016454
Fibula fracture	10016667
Foetal-maternal haemorrhage	10016871
Foot fracture	10016970
Forearm fracture	10016997

PT Term	Code
Fracture	10017076
Fracture delayed union	10017081
Fracture malunion	10017085
Fracture nonunion	10017088
Fractured sacrum	10017308
Gait disturbance	10017577
Gastric haemorrhage	10017788
Gastric ulcer haemorrhage	10017826
Gastric ulcer haemorrhage, obstructive	10017829
Gastritis alcoholic haemorrhagic	10017857
Gastritis haemorrhagic	10017866
Gastrointestinal haemorrhage	10017955
Gingival bleeding	10018276
Greenstick fracture	10018720
Haemarthrosis	10018829
Haematemesis	10018830
Haematocoele	10018833
Haematochezia	10018836
Haematoma	10018852
Haematospermia	10018866
Haematuria	10018867
Blood urine present	10018870
Haematuria traumatic	10018871
Haemoperitoneum	10018935
Haemoptysis	10018964
Haemorrhage in pregnancy	10018981
Haemorrhage intracranial	10018985
Haemorrhage subcutaneous	10018999
Haemorrhage subepidermal	10019001
Haemorrhagic cerebral infarction	10019005
Haemorrhagic disease of newborn	10019008
Haemorrhagic disorder	10019009
Haemorrhagic infarction	10019013
Haemorrhagic stroke	10019016
Haemothorax	10019027
Hand fracture	10019114
Henoch-Schonlein purpura	10019617
Hepatic haematoma	10019676

PT Term	Code
Hepatic haemorrhage	10019677
Hereditary haemorrhagic telangiectasia	10019883
Hip fracture	10020100
Humerus fracture	10020462
Hyphaema	10020923
Hypophosphataemia	10021058
Hyporeflexia	10021089
Ilium fracture	10021343
Impaired healing	10021519
Increased tendency to bruise	10021688
Injection site bruising	10022052
Injection site haematoma	10022066
Injection site haemorrhage	10022067
Intermenstrual bleeding	10022559
Internal fixation of fracture	10022576
International normalised ratio abnormal	10022592
International normalised ratio increased	10022595
Intracranial tumour haemorrhage	10022775
Intraventricular haemorrhage	10022840
Intraventricular haemorrhage neonatal	10022841
Keratomalacia	10023361
Kidney contusion	10023413
Kyphosis	10023509
Mallory-Weiss syndrome	10026712
Melaena	10027141
Menometrorrhagia	10027295
Mouth haemorrhage	10028024
Multiple fractures	10028200
Muscle haemorrhage	10028309
Muscle spasms	10028334
Muscular weakness	10028372
Musculoskeletal pain	10028391
Myalgia	10028411
Myocardial rupture	10028604
Nephritis haemorrhagic	10029132
Neuropathic arthropathy	10029326
Night blindness	10029404
Nipple exudate bloody	10029418

PT Term	Code
Nystagmus	10029864
Oesophageal haemorrhage	10030172
Oesophageal ulcer haemorrhage	10030202
Oesophageal varices haemorrhage	10030210
Oesophagitis haemorrhagic	10030219
Open fracture	10030527
Open reduction of fracture	10030682
Open reduction of spinal fracture	10030684
Ophthalmoplegia	10030875
Optic disc haemorrhage	10030919
Optic nerve sheath haemorrhage	10030941
Orbital haemorrhage	10031045
Osteomalacia	10031250
Osteoporosis	10031282
Osteoporotic fracture	10031290
Ovarian haematoma	10033263
Pancreatic haemorrhage	10033625
Pancreatitis haemorrhagic	10033650
Pathological fracture	10034156
Pelvic haematoma obstetric	10034248
Penile haemorrhage	10034305
Peptic ulcer haemorrhage	10034344
Pericardial haemorrhage	10034476
Perineal haematoma	10034520
Periorbital haematoma	10034544
Petechiae	10034754
Pharyngeal haemorrhage	10034827
Placenta praevia haemorrhage	10035121
Post abortion haemorrhage	10036246
Post-traumatic osteoporosis	10036315
Postpartum haemorrhage	10036417
Premature separation of placenta	10036608
Proctitis haemorrhagic	10036778
Prostatic haemorrhage	10036960
Prothrombin level abnormal	10037048
Prothrombin level decreased	10037050
Prothrombin time abnormal	10037057
Prothrombin time prolonged	10037063

PT Term	Code
Pulmonary alveolar haemorrhage	10037313
Pulmonary contusion	10037370
Pulmonary haemorrhage	10037394
Purpura	10037549
Purpura fulminans	10037556
Purpura neonatal	10037557
Purpura senile	10037560
Radius fracture	10037802
Rectal haemorrhage	10038063
Rectal ulcer haemorrhage	10038081
Renal haematoma	10038459
Renal haemorrhage	10038460
Respiratory tract haemorrhage	10038727
Respiratory tract haemorrhage neonatal	10038728
Retinal haemorrhage	10038867
Retroperitoneal haemorrhage	10038980
Rib fracture	10039117
Ruptured cerebral aneurysm	10039330
Scrotal haematoma	10039749
Senile osteoporosis	10039984
Short stature	10040600
Spinal compression fracture	10041541
Spinal fracture	10041569
Splenic haematoma	10041646
Splenic haemorrhage	10041647
Splinter haemorrhages	10041663
Sternal fracture	10042015
Stomatitis haemorrhagic	10042132
Stress fracture	10042212
Subarachnoid haemorrhage	10042316
Subarachnoid haemorrhage neonatal	10042317
Subcutaneous haematoma	10042345
Subdural haematoma	10042361
Subdural haematoma evacuation	10042363
Subdural haemorrhage	10042364
Subdural haemorrhage neonatal	10042365
Third stage postpartum haemorrhage	10043449
Thrombocytopenic purpura	10043561

PT Term	Code
Thrombotic thrombocytopenic purpura	10043648
Tibia fracture	10043827
Tongue haematoma	10043959
Tooth injury	10044043
Tooth malformation	10044046
Traumatic haematoma	10044522
Tremor	10044565
Ulna fracture	10045375
Umbilical haemorrhage	10045455
Upper gastrointestinal haemorrhage	10046274
Urinary bladder haemorrhage	10046528
Uterine haemorrhage	10046788
Vaginal haematoma	10046909
Vaginal haemorrhage	10046910
Varicose vein ruptured	10046999
Vascular purpura	10047097
Ventricle rupture	10047279
Vitamin A deficiency related conjunctival disorder	10047588
Vitamin A deficiency related corneal disorder	10047589
Vitreous haemorrhage	10047655
Vulval haematoma	10047756
Vulval haematoma evacuation	10047757
Withdrawal bleed	10047998
Wrist fracture	10048049
Xerophthalmia	10048221
Xerosis	10048222
Aneurysm ruptured	10048380
Atrial rupture	10048761
Myocardial haemorrhage	10048849
Nail bed bleeding	10048891
Spinal cord haemorrhage	10048992
Osteopenia	10049088
Fractured coccyx	10049164
Spinal epidural haemorrhage	10049236
Lip haemorrhage	10049297
Bone density decreased	10049470
Traumatic fracture	10049514
Anal haemorrhage	10049555

PT Term	Code
Urethral haemorrhage	10049710
Tumour haemorrhage	10049750
Pituitary haemorrhage	10049760
Shock haemorrhagic	10049771
Melaena neonatal	10049777
Tongue haemorrhage	10049870
Osteoporosis prophylaxis	10049904
Mediastinal haematoma	10049941
Cervical vertebral fracture	10049946
Lumbar vertebral fracture	10049947
Thoracic vertebral fracture	10049948
Cervix haematoma uterine	10050020
Cervix haemorrhage uterine	10050022
Urogenital haemorrhage	10050058
Application site bruise	10050114
Cerebral haemorrhage foetal	10050157
Spinal epidural haematoma	10050162
Spinal subdural haematoma	10050164
Application site purpura	10050182
Skin ulcer haemorrhage	10050377
Chronic gastrointestinal bleeding	10050399
Haematosalpinx	10050468
Scleral haemorrhage	10050508
Contusion	10050584
Lower gastrointestinal haemorrhage	10050953
Post procedural haemorrhage	10051077
Catheter site haemorrhage	10051099
Incision site haemorrhage	10051100
Puncture site haemorrhage	10051101
Parotid gland haemorrhage	10051166
Soft tissue haemorrhage	10051297
Carotid aneurysm rupture	10051328
Wound haemorrhage	10051373
Retinopathy haemorrhagic	10051447
Corneal bleeding	10051558
Haematoma infection	10051564
Testicular haemorrhage	10051877
Osteorrhagia	10051937

PT Term	Code
Urinary occult blood positive	10052287
Brain contusion	10052346
Large intestinal haemorrhage	10052534
Small intestinal haemorrhage	10052535
Meningorrhagia	10052593
Comminuted fracture	10052614
Induced abortion haemorrhage	10052844
Eyelid bleeding	10053196
Fracture displacement	10053206
Anticoagulant therapy	10053468
Traumatic haemorrhage	10053476
Vascular rupture	10053649
Growth retardation	10053759
Gastroduodenal haemorrhage	10053768
Cerebral haematoma	10053942
Vascular pseudoaneurysm ruptured	10053949
Epiphyseal fracture	10053962
Implant site haemorrhage	10053995
Vessel puncture site haemorrhage	10054092
Haemorrhagic tumour necrosis	10054096
Haemorrhoidal haemorrhage	10054787
Retroplacental haematoma	10054798
Hepatic haemangioma rupture	10054885
Pelvic haematoma	10054974
Pulmonary haematoma	10054991
Arteriovenous fistula site haemorrhage	10055123
Arteriovenous graft site haemorrhage	10055126
Arteriovenous fistula site haematoma	10055150
Arteriovenous graft site haematoma	10055152
Catheter site haematoma	10055662
Haemorrhagic transformation stroke	10055677
Haemorrhage	10055798
Haemorrhage coronary artery	10055803
Haemorrhage urinary tract	10055847
Postmenopausal haemorrhage	10055870
Haematoma muscle	10055890
Protein induced by vitamin K absence or antagonist II	10056243
Protein induced by vitamin K absence or antagonist II increased	10056247

PT Term	Code
Mediastinal haemorrhage	10056343
Anastomotic haemorrhage	10056346
Pituitary apoplexy	10056447
Intra-abdominal haematoma	10056457
Gastrointestinal ulcer haemorrhage	10056743
Body height decreased	10056812
Palpable purpura	10056872
Fracture debridement	10057147
Loss of proprioception	10057332
Ciliary body haemorrhage	10057417
Iris haemorrhage	10057418
Tonsillar haemorrhage	10057450
Ocular retrobulbar haemorrhage	10057571
Gastric varices haemorrhage	10057572
Fracture reduction	10057609
Cognitive disorder	10057668
Bloody discharge	10057687
Purpura non-thrombocytopenic	10057739
Peritoneal haematoma	10058095
Retroperitoneal haematoma	10058360
Spinal deformity	10058907
Thalamus haemorrhage	10058939
Putamen haemorrhage	10058940
Haemobilia	10058947
Acute haemorrhagic leukoencephalitis	10058994
Cullen's sign	10059029
Parathyroid haemorrhage	10059051
Papillary muscle haemorrhage	10059164
Intestinal haemorrhage	10059175
Haemorrhagic cyst	10059189
Adrenal haematoma	10059194
Infusion site bruising	10059203
Incision site haematoma	10059241
Intracranial haematoma	10059491
Haemorrhagic urticaria	10059499
Haemorrhagic ascites	10059766
Renal cyst haemorrhage	10059846
Anticoagulation drug level above therapeutic	10060320

PT Term	Code
Skin neoplasm bleeding	10060712
Mesenteric haemorrhage	10060717
Haematoma evacuation	10060733
Haemorrhagic ovarian cyst	10060781
Aortic rupture	10060874
Arterial haemorrhage	10060964
Cerebellar haematoma	10061038
Pelvic fracture	10061161
Genital haemorrhage	10061178
Haemorrhage foetal	10061191
Intra-abdominal haemorrhage	10061249
Large intestinal ulcer haemorrhage	10061262
Mucosal haemorrhage	10061298
Pelvic deformity	10061335
Scrotal haemorrhage	10061361
Traumatic intracranial haemorrhage	10061387
Upper limb fracture	10061394
Vitamin A deficiency eye disorder	10061412
Scrotal haematocoele	10061517
Small intestinal ulcer haemorrhage	10061550
Ulcer haemorrhage	10061577
Lower limb fracture	10061599
Coagulation factor IX level abnormal	10061770
Coagulation factor VII level abnormal	10061772
Coagulation factor X level abnormal	10061774
Occult blood positive	10061880
Fracture treatment	10061959
Haemorrhage neonatal	10061993
Intracerebral haematoma evacuation	10062025
Knee deformity	10062061
Tracheal haemorrhage	10062543
Tooth fracture	10062544
Bladder tamponade	10062656
Haemorrhagic diathesis	10062713
Thoracic haemorrhage	10062744
Naevus haemorrhage	10062955
Haematotympanum	10063013
Post procedural haematoma	10063188

PT Term	Code
International normalised ratio fluctuation	10063351
Circulating anticoagulant positive	10063576
Graft haemorrhage	10063577
Catheter site bruise	10063587
Pelvic haemorrhage	10063678
Implant site haematoma	10063780
Vulval haemorrhage	10063816
Implant site bruising	10063850
Uterine haematoma	10063875
Vessel puncture site bruise	10063881
Anal ulcer haemorrhage	10063896
Polymenorrhagia	10064050
Angina bullosa haemorrhagica	10064223
Thyroid haemorrhage	10064224
Skin haemorrhage	10064265
Umbilical cord haemorrhage	10064534
Haemorrhagic arteriovenous malformation	10064595
Breast haematoma	10064753
Tooth socket haemorrhage	10064946
Eyelid haematoma	10064976
Ulcerative keratitis	10064996
Coital bleeding	10065019
Haemophilic arthropathy	10065057
Spontaneous haematoma	10065304
Venous haemorrhage	10065441
Infusion site haematoma	10065463
Infusion site haemorrhage	10065464
Bronchial haemorrhage	10065739
Laryngeal haemorrhage	10065740
Ovarian haemorrhage	10065741
Spermatic cord haemorrhage	10065742
Ureteric haemorrhage	10065743
Vessel puncture site haematoma	10065902
Torus fracture	10066094
Avulsion fracture	10066184
Post procedural haematuria	10066225
Bone contusion	10066251
Lip haematoma	10066304

PT Term	Code
Impacted fracture	10066386
Basal ganglia haemorrhage	10067057
Liver contusion	10067266
Cerebral microhaemorrhage	10067277
Astringent therapy	10067372
Abdominal wall haematoma	10067383
Haemostasis	10067439
Myelomalacia	10067441
Bloody peritoneal effluent	10067442
Decreased vibratory sense	10067502
Intrapartum haemorrhage	10067703
Haemorrhagic erosive gastritis	10067786
Abdominal wall haemorrhage	10067788
Haemorrhagic hepatic cyst	10067796
Gastric occult blood positive	10067855
Aortic intramural haematoma	10067975
Aortic dissection rupture	10068119
Pharyngeal haematoma	10068121
Application site haematoma	10068317
Choroidal haematoma	10068642
Splenic varices haemorrhage	10068662
Umbilical haematoma	10068712
Bone density abnormal	10068789
Anorectal varices haemorrhage	10068925
Periprosthetic fracture	10069135
Abnormal withdrawal bleeding	10069195
Vaccination site haematoma	10069472
Vaccination site haemorrhage	10069475
Vaccination site bruising	10069484
Subgaleal haematoma	10069510
Paranasal sinus haematoma	10069702
Loss of anatomical alignment after fracture reduction	10069723
Intestinal haematoma	10069829
Lacrimal haemorrhage	10069930
Penile haematoma	10070656
Muscle contusion	10070757
Atypical femur fracture	10070884
Laryngeal haematoma	10070885

PT Term	Code
Subchorionic haemorrhage	10071010
Growth failure	10071095
Brain stem microhaemorrhage	10071205
Cerebellar microhaemorrhage	10071206
Procedural haemorrhage	10071229
Haemorrhagic vasculitis	10071252
Wound haematoma	10071504
Mesenteric haematoma	10071557
Post-traumatic punctate intraepidermal haemorrhage	10071639
Periorbital haemorrhage	10071697
Intraocular haematoma	10071934
Subretinal haematoma	10071935
Vitreous haematoma	10071936
Central nervous system haemorrhage	10072043
Fracture pain	10072132
Tooth pulp haemorrhage	10072228
Haemorrhagic thyroid cyst	10072256
Post transfusion purpura	10072265
Radiation associated haemorrhage	10072281
Atypical fracture	10072395
Subchorionic haematoma	10072596
Peripartum haemorrhage	10072693
Application site haemorrhage	10072694
Chronic pigmented purpura	10072726
Iliac artery rupture	10072789
Chance fracture	10073162
Brain stem haematoma	10073230
Penile contusion	10073352
Post procedural contusion	10073353
Eye contusion	10073354
Genital contusion	10073355
Cardiac contusion	10073356
Spleen contusion	10073533
Spinal subdural haemorrhage	10073563
Spinal subarachnoid haemorrhage	10073564
Bone marrow haemorrhage	10073581
Instillation site haematoma	10073609
Instillation site haemorrhage	10073610

PT Term	Code
Instillation site bruise	10073630
Epidural haemorrhage	10073681
Haemophilic pseudotumour	10073770
Osteochondral fracture	10073853
Neonatal gastrointestinal haemorrhage	10074159
Lymph node haemorrhage	10074270
Sacroiliac fracture	10074362
Gastrointestinal polyp haemorrhage	10074437
Traumatic haemothorax	10074487
Stoma site haemorrhage	10074508
Limb fracture	10074551
Spontaneous haemorrhage	10074557
Deep dissecting haematoma	10074718
Hyperfibrinolysis	10074737
Oral mucosa haematoma	10074779
Spinal fusion fracture	10074807
Arterial intramural haematoma	10074971
Eyelid contusion	10075018
Nasal septum haematoma	10075027
Administration site bruise	10075094
Administration site haematoma	10075100
Administration site haemorrhage	10075101
Internal haemorrhage	10075192
Activated partial thromboplastin time ratio abnormal	10075284
Activated partial thromboplastin time ratio fluctuation	10075286
Activated partial thromboplastin time ratio increased	10075287
Aponeurosis contusion	10075330
Cerebral aneurysm perforation	10075394
Grey Turner's sign	10075426
Medical device site bruise	10075570
Medical device site haematoma	10075577
Medical device site haemorrhage	10075578
Acute haemorrhagic ulcerative colitis	10075634
Carotid artery perforation	10075728
Aortic perforation	10075729
Lower limb artery perforation	10075730
Iliac artery perforation	10075731
Arterial perforation	10075732

PT Term	Code
Venous perforation	10075733
Cerebral artery perforation	10075734
Vertebral artery perforation	10075735
Basilar artery perforation	10075736
Renal artery perforation	10075737
Splenic artery perforation	10075738
Femoral artery perforation	10075739
Subclavian artery perforation	10075740
Superior vena cava perforation	10075741
Inferior vena cava perforation	10075742
Subclavian vein perforation	10075743
Iliac vein perforation	10075744
Femoral vein perforation	10075745
Mucocutaneous haemorrhage	10076048
Spinal cord haematoma	10076051
Haemorrhagic necrotic pancreatitis	10076058
Oral blood blister	10076590
Chest wall haematoma	10076597
Subarachnoid haematoma	10076701
Periventricular haemorrhage neonatal	10076706
Basal ganglia haematoma	10077031
Vein rupture	10077110
Surgical fixation of rib fracture	10077270
Periosteal haematoma	10077341
Haemorrhagic breast cyst	10077443
Oesophageal intramural haematoma	10077486
Vascular access site haemorrhage	10077643
Vascular access site haematoma ^a	10077647
Vascular access site rupture	10077652
Joint microhaemorrhage	10077666
Vascular graft haemorrhage	10077721
Vascular access site bruising	10077767
Bursal haematoma	10077818
Intestinal varices haemorrhage	10078058
Oral contusion	10078170
Extra-axial haemorrhage	10078254
Costal cartilage fracture	10078358
Lisfranc fracture	10078749

PT Term	Code
Traumatic intracranial haematoma	10079013
Retinal aneurysm rupture	10079121
Bronchial varices haemorrhage	10079163
Fracture blisters	10079423
Achenbach syndrome	10079562
Metaphyseal corner fracture	10079667
Anal fissure haemorrhage	10079765
Fracture infection	10079813
Subchondral insufficiency fracture	10079864
Eye haematoma	10079891
Haemorrhagic adrenal infarction	10079902
Peripheral artery aneurysm rupture	10079908
Paranasal sinus haemorrhage	10080108
Pseudofracture	10080404
Osteophyte fracture	10080550
Gastrointestinal vascular malformation haemorrhagic	10080561
Subgaleal haemorrhage	10080900
Maisonneuve fracture	10081343
Hypophosphataemic osteomalacia	10081362
Fothergill sign positive	10081749
Growth disorder	10081945
Puncture site haematoma	10081957
Puncture site bruise	10082035
Cerebral cyst haemorrhage	10082099
Pulmonary haemorrhage neonatal	10082194
Blood loss anaemia	10082297
Pathological fracture prophylaxis	10082364
Subendocardial haemorrhage	10082459
Acquired factor IX deficiency	10082747
Extradural haematoma evacuation	10082797
Pathological tooth fracture	10082930
Pharyngeal contusion	10083176
Anticoagulant-related nephropathy	10083346
Urinary bladder haematoma	10083358
Subcapsular hepatic haematoma	10083383
Subcapsular splenic haematoma	10083384
Subcapsular renal haematoma	10083385
Oral purpura	10083533

PT Term	Code
Orbital haematoma	10083565
Spinal fracture treatment	10083586
Bullous haemorrhagic dermatosis	10083809
Pancreatic pseudocyst haemorrhage	10083813
Immune thrombocytopenia	10083842
Haemangioma rupture	10084040
Vascular anastomotic haemorrhage	10084092
Intratumoural haematoma	10084177
Antiplatelet reversal therapy	10084904
Urinary occult blood	10084960
Omental haemorrhage	10085045
Haemorrhagic occlusive retinal vasculitis	10085070
Haemorrhagic gastroenteritis	10085136
Scleral haematoma	10085163
Jugular vein haemorrhage	10085298
Gastrointestinal anastomotic haemorrhage	10085369
Heavy menstrual bleeding	10085423
Abnormal uterine bleeding	10085424
Gallbladder haematoma	10085893
Haemorrhagic cerebellar infarction	10085944
Peripheral exudative haemorrhagic chorioretinopathy	10086195
Hyper gammaglobulinaemic purpura of Waldenstrom	10086403
Intracranial haemorrhage neonatal	10086946
Hepatic artery haemorrhage	10087132

^aThe list of PTs in Appendix G was created based on MedDRA Version 25.0; as of MedDRA Version 26.0, LLT Peripheral artery haematoma has been changed from PT Peripheral artery haematoma to PT Vascular access site haematoma.
